Each participating laboratory will be allocated with a specific number of samples to be collected, stratified by age (in years) and sex. Tubes and labels with a code indicating the laboratory number, age and sex of the patient's sample, will be provided by Sciensano. For each participant, we will collect (if possible) 2ml leftover serum, with a minimum of 0.5ml. For pediatric samples (children <5y of age), minimal required sample volume is 0.2ml. Each sample will be divided in two tubes by the laboratory to ensure minimal freeze-thaw cycles. Depending on the number of samples to collect, every laboratory will be provided with the corresponding number of tubes and labels as well as some additional tubes and labels, in case of errors.

Participating laboratories will be instructed to keep the samples in a refrigerator (4-8°C) for no more than 4 days following centrifugation, and to then store them at -20°C until collection by Sciensano.

Sciensano will organize two transports of samples at -20° C (on dry ice) per participating laboratory, one 6 months after the start of the collection period, and one at the end. Additional transports might be organized in consultation with Sciensano if deemed necessary by the laboratory based on its storage capacity. At Sciensano, samples will be stored at -80° C.

The serum bank will be stored and managed by Sciensano. Samples will be registered within the biobank "Sciensano Biobank module WD 11 prospectief" (FAMHP reference number: BB190137), according to the Sciensano standardized operational procedure for biobanks management. Samples will be stored at Sciensano for a period of 20 years for potential use in future research studies. After 20 years they will be destroyed, with the approval of the biobank professional manager.

Sample analysis

Sciensano will organize the transport to the laboratory in charge of the analyses, with samples kept at -20°C (on dry ice) during transit. Once at Sciensano, all samples will be kept at -80°C. Laboratory analysis will be performed using the appropriate testing methodology as defined in agreement with the respective National Reference Center.

Samples will be tested either at the respective National Reference Center, or, in case of availability of multiplex testing, at the Service of immune response at Sciensano.

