Residual human body material samples (as defined by the "HBM law" of 19.12.2008 and for which the presumed donor consent principle applies) that were already used in the *Seroprevalentiestudie* van infectieziekten in België 2013–2015 (i.e. a past study with ethical committee registration number: BE300201316922) and stored in the *Sciensano Biobank module WD 11 prospectief* (FAMHP reference: BB190137), were collected using a similar methodology. These samples will be re-tested in the current study to validate the current testing approach and enable cautious longitudinal data comparison.

Data collection

Data transfer

1. Information transferred from participating laboratories to Sciensano

Laboratories will share, on a monthly basis, anonymized information about the samples they have collected so far (unique sample code, age, sex and arrondissement) through a password-protected Excel document. Based on lab preference, data will be sent through a Secured Filed Transfer Protocol (sFTP) or a dedicated mailbox with restricted access, specifically set up for this project.

2. Information transferred from laboratory in charge of testing to Sciensano

Serology test results will be reported through spreadsheets using the unique sample codes. Data will be shared through e-mail or, if laboratory testing is done at Sciensano, by storage in a dedicated folder on the Sciensano file server with access restricted to the study team and laboratory responsible.

Data collection procedure

Collection of data at labs participating in sample collection

Participating laboratories will collect the samples requested and label them with a unique sample code. The study sample code cannot be linked back to the patient, thereby ensuring anonymity in the further process.

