Participating laboratories will fill in a password-protected Excel document containing an overview of the pre-filled sample codes (Appendix 2). In the first tab of the document, the laboratory fills for every included sample date of birth, gender and postal code of the patient whose blood/serum sample was labelled with the corresponding sample code. Using this information, the built-in validation rules of the spreadsheet will flag potential duplicates and ask the lab collaborator to verify and exclude samples from the same patient. The date of birth and postal code variables will then be automatically converted into age and arrondissement on a second tab of the Excel-sheet. Only the second tab, containing sample code, age (in years), gender and arrondissement, will be transferred to Sciensano. This procedure allows to avoid multiple samples from the same patient being included (since the sample collection will run over several months) whilst at the same time ensuring only anonymous data are shared with Sciensano. Laboratories will be asked to destroy the original Excel files after the collection period has ended.

A verification will be performed by an epidemiologist of Sciensano to ensure that information on age and gender collected through the Excel document matches the sample labels.

The final serum bank and the data files will be the responsibility of Sciensano.

Laboratories will be invited to an online meeting beforehand, outlining the study methodology and sampling procedure. A recording of the meeting as well as additional written documentation will be available afterwards. A project web-page on the Sciensano website will be developed to enable participating laboratories to access useful information as well as contact details in case of further questions.

Collection of data at laboratory in charge of testing

Laboratory testing results will be communicated to the study team through an Excel file only containing unique sample codes and test results, to ensure a maximum protection of data. The file will be stored at Sciensano on a secured and confidential file server. Since the data are anonymized, it will not be possible to link serological results to specific individuals, and therefore, no individual feedback will be provided.

Data analysis

General

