For each pathogen studied, we will calculate crude prevalence of seronegative, equivocal (if applicable) and seropositive results for Belgium. Since all collected samples will be tested for a certain pathogen by a single laboratory, we avoid any potential inter-laboratory variability in testing methodology. We assume that differences observed between laboratories reflect geographical variation rather than laboratory artifacts. However, since laboratories serve patients residing outside their province, the actual geographical distribution of samples may deviate from the intended stratification. To address this discrepancy, post-stratification weights will be applied to adjust for the spatial disparity between the data and the Belgian population. Moreover, seroprevalences will be adjusted for test sensitivity and specificity for the pathogen under investigation.

Statistical analysis will be done with R. Dummy tables are presented in Appendix 3. The specific analysis performed for each of the pathogens will be stored in an R file, containing explanation of the analysis. For each pathogen, these files will be stores in a secured folder at Sciensano.

Measles

For measles, measles vaccine target groups will additionally be defined as those targeted by measles vaccination (at least 1 year old and born in or after 1985) versus those not targeted (born before 1985, or not yet 1 year old at time of sampling). Within the measles vaccine-targeted group, two subgroups will be defined, with the 2-10 year olds as the ones targeted by minimal 1 dose and the 11-40 year olds as the ones targeted by 2 doses. The association between seronegativity and age group, sex, and province will be estimated using log binomial regression per measles vaccine target group. Adjusted prevalence ratios (aPR) and 95% confidence intervals (CI) will be calculated. P-values <0.05 will be considered significant.

The geometric mean titers (GMTs) for anti-measles IgG will be calculated and adjusted for clustered sampling and standardized for age, sex and population per province according to the Belgian population structure in 2025. The 95% confidence intervals (95%CI) will be estimated. Differences in GMTs between sex, region and age group will be assessed with the adjusted Wald chi-square test.

Quality assurance

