Tetanus	anti-TTIgG	 All ages, incl. 65+ 	Classic marker of vaccination coverageUnclear population immunity in elderly	
Diphtheria	Anti-DT	•	 2022-2023 outbreak in Belgium including 1 fatal case (16y) Emergence of macrolide-resistant C. Diphtheria C. Ulcerans infections in elderly 	Risk groups Belgium 2014- 2016 Belgium, 2012
CMV	anti-CMV IgG	all ageswomen reproducti ve age	 Ph3 clinical trials vaccine underway cCMV big public health impact 	Belgium 2002,2006

Appendix 2

Data collection sheet for laboratories (only seen by laboratories)

Laboratory	Nb	1
------------	----	---

Unique code	Sample date	Date of birth	Gender	Postcode
Laboratory/gender/age				
Data collection sheet delivered i	from laboratories to Scier	nsano		
Laboratory Nb 1				
Unique code	Sample A date	\ge Ge	nder Arro	ondissement
Laboratory/gender/age				

Appendix 3

Dummy tables

1. Study population characteristics

Variable	Category	N (%) – Study population	N (%) – Belgian population
Age	1-4 yo		
	5-9 yo		
	10-14 yo		
	15-19 yo		
	20-29 yo		
	30-39 yo		
	40-49 yo		
	50-59 yo		
	60-69 yo		
	≥ 70 yo		
Sex	Female		
	Male		
Provinces	Antwerp		
	West Flanders		
	East Flanders		
	Limburg		
	Flemish Brabant		
	Walloon Brabant		
	Hainaut		
	Namur		
	Liege		
	Luxembourg		
	Brussels		

2. Seroprevalence by Demographic Characteristics – one table per pathogen

Characteristic	n tested	n seropositive	% Seropositive (95% CI)
Age group (years)			
Sex			
Region/provinces			

3.	Comparison of Seroprevalence over time (with previous seroprevalence study) – one table
	per pathogen

Birth cohort	Time point	n tested	n seropositive	% Seropositive (95% CI)
Targeted by measles vaccination	Study 2013/2015			
	Study 2025/2026			
Not targeted by measles vaccination	Study 2013/2015			
	Study 2025/2026			

4. Log binomial regression analysis (Prevalence Ratios) – one per pathogen

Variable	Adjusted Prevalence Ratios (95% CI)	p-value
Age		
Sex		
Region/provinces		

Appendix 4

Scientific steering committee – Composition

Function/entity	Expertise	Number of representatives
FOD Volksgezondheid (federal authorities)	Public Health	1
DepZorg (regional authorities)	Public Health	1
AViQ (regional authorities)	Public Health	1
Vivalis (regional authorities)	Public Health	1
ONE (regional entity)	Public Health (vaccination)	1
University of Hasselt – University of Antwerpen	Biostatistics	2
University of Gent (UGent) – University Hospital of Gent (UZ Gent)	Infectious diseases (adults)	1

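### Testing at one laboratory does not rule out run effects: mix collecting laboratories and survey years across runs, and return run identifiers with the results

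*Protocol*

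**What the plan says.** Five places in the protocol bear on this point.

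- **Data analysis – General:** "Since all collected samples will be tested for a certain pathogen by a single laboratory, we avoid any potential inter-laboratory variability in testing methodology". The next sentence reads: "We assume that differences observed between laboratories reflect geographical variation rather than laboratory artifacts".
- **Sample analysis:** of the stored 2013–2015 sera, "These samples will be re-tested in the current study to validate the current testing approach and enable cautious longitudinal data comparison".
- **Sample collection and transport:** each collecting laboratory's samples come in two transports, "one 6 months after the start of the collection period, and one at the end", with more if storage requires. The labels are "Tubes and labels with a code indicating the laboratory number, age and sex of the patient's sample", so the code shows where a tube comes from.
- **Data collection procedure:** results return to the study team "through an Excel file only containing unique sample codes and test results".
- **Appendix 3, dummy table 3:** seroprevalence is set out for the 2013/2015 and 2025/2026 studies, without saying whether the older rows hold original or re-tested results.

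The protocol states no order of testing, no mixing of laboratories or surveys within runs, and no adjustment for run.

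**The concern.** The two sentences under Data analysis – General do not follow from each other. Testing everything in one place removes differences between testing laboratories. It does nothing about differences between runs, plates or kit lots inside that place, so it cannot by itself justify reading every difference between collecting laboratories as geography.

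The same gap affects the comparison over time. Re-testing the stored sera separates a change of assay from a change in the population only if old and new sera share runs, or if run effects can be estimated.

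The results exposed are the geographical and trend objectives, the prevalence ratios by province and the comparison of geometric mean titres by region. All depend on titre differences, most of them around the fixed 120 IU/ml cut-off. If run coincided with laboratory or survey, no later analysis could separate the two. With only codes and results in the file, the analysts could not even look for the problem.

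**Working it through.** **1. The plan's own figures.** Taking the largest count per age group over the three pathogens in Appendix 5, Table 3 gives 450 + 450 + 300 + 450 + 450 + 750 + 1,050 = 3,900, as stated. Table 4 gives measles half-widths of 0.82% nationally (3,900) and 1.69% regionally (1,300). A simple binomial half-width, 1.96 × √(p(1−p)/n) at p = 0.9025, gives 0.93% and 1.61%. The stated values are simulation-based, so I infer no error and use them as yardsticks.

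**2. From a titre shift to a seroprevalence shift.** Overall measles seroprevalence is 0.902–0.903 (Table S1); I use 0.903. Assume log-normal titres with SD s of ln titre. The documents give no s, so I take 0.8 to 1.5. If all titres in a set of runs read at a fraction f of their true value, then

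change = Φ(z + ln f / s) − 0.903, with z = Φ⁻¹(0.903).

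| Reading | s = 0.8 | s = 1.2 | s = 1.5 |
|---|---|---|---|
| 10% low (f = 0.90) | −2.46 points | −1.59 | −1.26 |
| 5% low (f = 0.95) | −1.15 points | −0.75 | −0.60 |

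The geometric mean titre moves by the full 5% or 10%. On the seronegativity scale, a 10% low reading across a whole comparison group gives a ratio of (9.7 + 1.26)/9.7 = 1.13 to (9.7 + 2.46)/9.7 = 1.25 with no true difference.

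**3. Against the right precision.**

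- *Shift over a whole survey.* A 10% shift (1.26 to 2.46 points) exceeds 0.82% throughout. For a difference between two surveys each as precise as this one, the half-width is √2 × 0.82 = 1.16 points, still below 1.26. A 5% shift (0.60 to 1.15) straddles 0.82 and stays just under 1.16.
- *Shift in some laboratories only.* The stated regional half-width is 1.69%. The 10% shift at s = 1.2 (1.59) is below it, and at s = 0.8 (2.46) above it. For an equal-sized province, 3,900/11 ≈ 355 sera, the binomial half-width is 1.96 × √(0.903 × 0.097/355) ≈ 3.1 points, wider than any shift in the table.

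**4. False trends.** Suppose all old and all new sera sit in separate runs that differ by 10%, with no true change. At a base of 0.902 and s of 0.8 to 1.5, a two-sided z test at 0.05 is significant with probability 29% to 96%, for 1,500 to 3,900 re-tested sera. For 5% it is 10% to 40%. The number of re-tested sera is an assumption.

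**5. What mixing buys.** In 2,000 simulated surveys (11 equal provinces, 90 sera per run, s = 1.0, no true difference), a chi-square test across provinces rejected in 16% to 65% of surveys when runs were filled in province order. It rejected in 4% to 6% when sera were mixed at random. The scenarios were run-to-run SDs of 10% or 20%, or 10% with a linear drift of 20% or 30%. The layout and drift sizes are assumptions that show the mechanism, not a forecast.

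**The case against.** The strongest reply is that the protocol is silent on run order; it does not say that runs will be unmixed. It leaves testing methodology to agreement with the National Reference Center, and a laboratory procedure may already cover layout and lot changes. That stands: the confounding is a possibility left open.

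A reader might go further and infer that sera will be tested box by box, so that run is practically the same as laboratory. The documents do not support this. The figure 3,900/52 = 75 per laboratory, near one plate if a plate takes 80–90, requires all 52 invited laboratories to join with equal shares, while allocation is to follow population density. Two transports would bring about 37 per shipment. With 52/11 ≈ 5 laboratories per province, and patients who live outside their laboratory's province, independent run shifts would partly average out.

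Nor do the documents say that the stored sera will form their own runs, or that dummy table 3 will hold the original 2013–2015 results. The re-testing is introduced to allow a comparison over time that the protocol itself calls cautious, so re-tested results are the natural reading.

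Accreditation, validated assays, confirmatory tests and the sensitivity and specificity adjustment are real safeguards, but none is described as specific to a run. They leave the gap between premise and assumption where it was.

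**Conclusion.** The point holds as a worthwhile, cheap improvement. The protocol's assumption that laboratory differences are geographical is stronger than the reason given for it, and the results file as described would leave that assumption untestable.

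The size is material for a 10% shift over a whole survey's runs: 1.3 to 2.5 points against ±0.82% nationally. It is not clearly material for a 5% shift (0.6 to 1.15 points). For a shift confined to some laboratories it depends on the titre spread, when set against the regional ±1.69%. It would therefore be wrong to say that any modest drift exceeds the stated precision, or that the geographical and trend results will be artefacts. Titre SD and drift size are assumptions throughout; the documents give neither.

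**What to change.** - **Sample collection and analysis:** allocate sera to plates in random order, balanced over collecting laboratory, age group and survey, with the re-tested 2013–2015 sera on the same plates as the new sera. Start measles testing once the final transport is in; the Timeline already places the milestone for completed testing (M5) after that for completed collection (M4).
- **Data collection procedure:** add run or plate, kit lot and test date to the results file. None of these identifies a patient.
- **Data analysis – General:** replace the assumption about laboratory differences with a check for run and collecting-laboratory effects.
- **Appendix 3, dummy table 3:** state that the 2013/2015 rows use the re-tested results. Report the shift from original to re-test separately, as the joint effect of assay change and storage.

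The cost is a plate map, sorting time, and no measles testing before the last transport. No extra sera are needed. Neutral codes are not required; because the labels carry the laboratory number, they would mean relabelling or a masked work list. Mixing runs does not remove differences that arise at collection or the ageing of the stored sera, and the report should say so.

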For measles, the most recent national serological survey was conducted in 2013. To evaluate the sample size needed to estimate the current seroprevalence by age, we use a cohort-based modelling approach to project immunity levels to 2025. This model incorporates historical vaccination coverage, age of vaccination and waning immunity, following methods described by Hens et al. (2015) and Abrams et al. (2014) (30,31). The aim was to obtain both overall and agegroup-specific seroprevalence estimates with a precision of +-2% (width of confidence interval max. 4%). To ensure sufficient sample size of the serumbank for pathogens other than measles, these calculations were repeated for 2 additional pathogens. The additional pathogens (CMV and Hepatitis B) were selected based on their seroprevalence patterns in the population who differ importantly from the measles seroprevalence patterns.

Appendix 5 contains the full methodology and results. With a total sample size of 3,900 samples, precision of overall national seroprevalence estimates for all 3 pathogens would be <2% (and even <1% for measles and Hepatitis B). Not all agegroup-specific estimates would have <2% precision, but all are within acceptable ranges (all <3% precision for measles). To obtain equal precision in the region-specific estimates, similar absolute number of samples would need to be collected from Flanders, Walllonia and Brussels. However, as both the population size as well as

the number of labs in Brussels is much smaller than in Flanders, this is deemed unfeasible. We therefore plan a pragmatic approach and adjust the regional allocation to reflect practical constraints and the actual number of participating laboratories, accepting wider confidence intervals in Brussels. The final distribution of samples by agegroup is then presented in Table 1.

Table 1. Samples distribution - National

Age groups	Number of samples - National
1-4yo	450
5-9yo	450
10–14yo	300
15-19yo	450
19-31yo	450
31-40yo	750
40-65yo	1050
Total	3900

Sample collection and analysis

Sample collection and transport

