To ensure sufficient precision for all pathogens, we selected the maximum number of samples per age group across the three pathogens as the final recommendation. This results in a total of 3,900 samples nationally, which we divide equally across the three regions, yielding 1,300 samples per region.

Table 4 reports the expected precision of the overall seroprevalence estimates under this allocation. At the national level (3,900 samples per pathogen), the expected precision is 0.82% for measles, 0.85% for hepatitis B, and 1.69% for CMV. At the regional level (1,300 samples per region), expected precision decreases slightly to 1.69% for measles, 1.45% for hepatitis B, and 2.64% for CMV, still within acceptable bounds.

Age group	Measles	НерВ	CMV
1-4yo	5%	5%	15%
5-9yo	15%	15%	5%
10-14yo	5%	10%	10%
15-19yo	15%	5%	10%
19-31yo	15%	10%	10%
31-40yo	20%	25%	15%
40-65yo	25%	30%	35%
Precision	0,88%	0,74%	1,52%

Table 2. Optimal proportion of samples per age group for measles, hepatitis B, and CMV based on national-level simulations.

	Measles	НерВ	CMV	National	Regional
1-4yo	150	150	450	450	150
5-9yo	450	450	150	450	150
10-14yo	150	300	300	300	100
15-19yo	450	150	300	450	150
19-31yo	450	300	300	450	150
31-40yo	600	750	450	750	250
40-65yo	750	900	1050	1050	350
Total	3000	3000	3000	3900	1300

Table 3. Absolute number of samples per age group, assuming 3,000 samples per pathogen. The final allocation (bold values) corresponds to the highest required count across pathogens, resulting in a total of 3,900 samples nationally (or approximately 1,300 per region).

	Measles	НерВ	CMV
National	0,82%	0,85%	1,69%
Regional	1,69%	1,45%	2,64%

Table 4. Expected precision (half-width of the 95% simulation-based confidence interval) for overall seroprevalence estimates under the final allocation. National precision is based on 3,900 samples; regional precision is based on 1,300 samples per region.

Precision by age - national allocation

_	.=			
Age group	Allocation	Measles	НерВ	CMV
1-4yo	450	2,25%	0,50%	4,23%
5-9yo	450	2,61%	0,53%	3,25%
10-14yo	300	1,76%	0,63%	3,50%
15-19yo	450	1,95%	0,73%	3,14%
19-31yo	450	2,88%	1,20%	2,94%
31-40yo	750	2,40%	1,51%	2,78%
40-65vo	1050	1,25%	1.42%	3.02%

Table 5. Expected precision (half-width of the 95% simulation-based confidence interval) for prevalence estimates of each age group under the final allocation.

4. References of Appendix 5

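### Seroprevalence is to be weighted for geography only although the age quotas are deliberately disproportionate, so all-age summaries would depend on the quotas

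*Protocol*

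**What the plan says.** The estimation of seroprevalence is set out under Data analysis, General, for every pathogen studied. The first step is "we will calculate crude prevalence of seronegative, equivocal (if applicable) and seropositive results for Belgium". Because laboratories also serve patients from outside their province, "post-stratification weights will be applied to adjust for the spatial disparity between the data and the Belgian population". Finally, "seroprevalences will be adjusted for test sensitivity and specificity for the pathogen under investigation". Age does not appear among the weighting variables.

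The Measles subsection that follows treats the geometric mean titres (GMTs) differently. They are to be "standardized for age, sex and population per province according to the Belgian population structure in 2025".

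The age quotas are in the Sample size section: "The final distribution of samples by agegroup is then presented in Table 1". Appendix 5, Conclusions, explains their origin: "we selected the maximum number of samples per age group across the three pathogens as the final recommendation". The same section states what the design is expected to deliver nationally: "the expected precision is 0.82% for measles, 0.85% for hepatitis B, and 1.69% for CMV".

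**The concern.** Quotas built as a maximum over three pathogens are not proportional to the population. A national, regional or by-sex percentage that pools ages without age weights then averages over the quota age mix, not the Belgian one. Spatial weights cannot repair this if laboratories work to similar age quotas. For a marker that rises with age, the pooled figure is pulled towards the over-sampled children.

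The contrast with the GMTs makes this more than a detail left open. Age standardisation is written down for the titre summary, and only spatial weighting is written down for seroprevalence. An analysis plan that follows the text would carry the mismatch forward.

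The comparison over time is also exposed. Dummy table 3 (Appendix 3) sets pooled percentages from 2013/2015 beside those from 2025/2026 within two broad vaccine-target strata. Appendix 5, section 1.3 says the 2013 survey over-sampled children and adolescents. A different age mix within a stratum could look like a change in immunity.

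**Working it through.** **1. The plan's own figures.** The row maxima of Appendix 5 Table 3 sum to 450 + 450 + 300 + 450 + 450 + 750 + 1,050 = 3,900, as stated. For overall precision, let h_i be the Table 5 half-width and n_i the quota in age group i, with N = 3,900. The half-width of a quota-weighted proportion is √Σ(n_i/N)²h_i². The simple binomial value is 1.96√(p(1-p)/3,900), with p from Tables S1-S3.

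| | Stated | From Table 5 | Simple binomial |
|---|---|---|---|
| Measles (p = 0.903) | 0.82% | 0.81% | 0.93% |
| Hepatitis B (p = 0.055) | 0.85% | 0.52% | 0.72% |
| CMV (p = 0.348) | 1.69% | 1.28% | 1.50% |

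Measles reproduces. Hepatitis B and CMV do not reproduce as quota-weighted proportions. Their stated values exceed even the binomial ones, with variance ratios of about 1.41 and 1.28. That is what age weighting would produce, though it does not prove it.

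**2. The planning estimator.** Appendix 5, section 1.5 estimates overall seroprevalence through a GAM. In Tables S1-S3 the overall value hardly moves between survey-based, population-based and uniform age structures: measles 0.902-0.903, hepatitis B 0.054-0.055, CMV 0.347-0.349. A proportion without age weights would move with the age mix. The planned precision therefore belongs to an age-adjusted quantity.

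**3. Age shares.** The population shares are in a figure that is not shown. Assumption: equal share per year of age over 1-64, that is 4, 5, 5, 4, 12, 9 and 25 years of 64, reading each upper limit from 15-19 on as exclusive.

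- Groups up to 19: 1,650/3,900 = 42.3% of samples, against 18/64 = 28.1%.
- 40-65: 1,050/3,900 = 26.9% of samples, against 25/64 = 39.1%.

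**4. Age profiles.** Table 5 gives "Expected precision (half-width of the 95% simulation-based confidence interval) for prevalence estimates of each age group under the final allocation". Solving p_i(1-p_i) = n_i(h_i/1.96)², with the upper root for measles and the lower root for the other two, gives approximate prevalences (%):

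| Age group | Measles | Hepatitis B | CMV |
|---|---|---|---|
| 1-4 | 93.7 | 0.3 | 29.9 |
| 5-9 | 91.3 | 0.3 | 14.5 |
| 10-14 | 97.5 | 0.3 | 10.7 |
| 15-19 | 95.3 | 0.6 | 13.3 |
| 19-31 | 89.1 | 1.7 | 11.4 |
| 31-40 | 87.1 | 4.7 | 18.5 |
| 40-65 | 95.5 | 5.9 | 47.3 |

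**5. Bias** = Σ(n_i/N)p_i - Σw_i p_i, with w_i the population share:

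- Measles: 92.59 - 92.83 = -0.24 points.
- Hepatitis B: 2.84 - 3.37 = -0.53 points.
- CMV: 25.1 - 27.9 = -2.8 points.

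**6. Sensitivity.** The inverted profiles give overall values of 0.93, 0.034 and 0.28, not the stated 0.903, 0.055 and 0.348. Scaling p_i(1-p_i) by 1.303 (measles) and 1.575 (hepatitis B) restores the stated values. The bias is then -0.34 and -0.87 points. CMV cannot be scaled this way. Raising its 40-65 prevalence to about 0.65 reaches 0.348 and gives a bias of about -4.9.

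The population shares were then varied: under 19 from 24 to 32%, 19-39 from 29 to 38%, 40-64 from 36 to 44%. Unscaled and scaled profiles together give:

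- Measles: -0.75 to +0.16, against ±0.82.
- Hepatitis B: -1.28 to -0.34, against ±0.85.
- CMV (unscaled): -4.4 to -1.75, against ±1.69.

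One more extreme mix (28% under 19, 28% at 19-39, 44% at 40-64) brings measles level with its precision. The scaled group means are 92.57, 83.85 and 94.08, so the standardised value is 0.28 × 92.57 + 0.28 × 83.85 + 0.44 × 94.08 = 90.79, and 89.96 - 90.79 = -0.83.

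**The case against.** The weighting sentence answers one specific problem, patients who live outside a laboratory's province, and does not say that age is excluded. Pathogen-specific analyses are left to documented R files, an analysis plan may exist, and dummy table 1 already sets the sample's age distribution beside the Belgian one. This has some weight. However, the text gives a rule with a stated purpose, and the adjacent rule for GMTs names age. This is a stated rule that does not fit the design, not a mere omission.

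The other objections limit the scope, and they stand:

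- The first-priority result is age-specific measles seroprevalence. Quotas between age groups do not bias it, and the regression adjusts for age group.
- Measles is the only pathogen committed for analysis. Hepatitis B and CMV served to size the bank, from 1993 and 2011 data, and the steering committee has still to choose further pathogens.
- Dummy table 3 compares surveys within vaccine-target strata, not as one all-age figure. An effect of age mix there is possible but not demonstrated.

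A reader might infer that the national estimates in general are biased by more than their stated precision. The documents do not support that. For measles, immunity differs little by age and over- and under-sampled groups partly offset each other.

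**Conclusion.** The mismatch is real and confined to all-age summaries: national, regional and by sex. As written, these depend on the quotas and do not estimate the quantity behind Table 4. The bias clearly exceeds stated precision for CMV, is borderline for hepatitis B, and for measles is well inside it at the central values, reaching it only under an extreme assumed age mix.

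The sizes rest on assumed population shares, on the approximate inversion of Table 5, and on quotas spread similarly over the country. The direction for CMV and hepatitis B is firm over everything tried; for measles even the sign is not. The inconsistency itself needs none of these assumptions.

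**What to change.** In Data analysis, General, state that all overall, regional and by-sex seroprevalence estimates will be post-stratified or raked by age group, sex and province to the 2025 Belgian population aged 1-65, the sampled range in Table 1. This is the same standard as for the GMTs. In addition:

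- Label these figures as estimates for ages 1-65. Table 1 has no samples below 1 or above 65, and age weights cannot fill unsampled strata.
- Apply one age standard to both surveys in the comparison over time.
- Keep crude n and % as descriptive columns only.

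The cost is small. Age, sex and arrondissement are already collected, and sampling does not change. Variance rises slightly: with the equal-year shares, √Σw_i²h_i² from Table 5 gives 0.86% for measles (0.81% with quota shares), 0.64% for hepatitis B (0.52%) and 1.45% for CMV (1.28%).
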